APPENDIX III A: LENALIDOMIDE EDUCATION AND COUNSELING GUIDANCE DOCUMENT FOR FEMALE SUBJECTS

To be completed prior to each dispensing of lenalidomide.

Protocol Number: ACNS1022

COG Patient ID#: _____ DOB: _____ / _____ / _____ (mm/dd/yyyy)

(Check the appropriate box to indicate risk category)

FCCBP (Female children of childbearing potential): female child who: 1) has achieved menarche or breast development in Tanner Stage 2 or greater, and 2) has not undergone a hysterectomy or bilateral oophorectomy.

Note: Amenorrhea following cancer therapy does not rule out childbearing potential

FCNCBP (Female Children Not of Childbearing Potential): female child who: 1) has not experienced menarche or breast development has not reached Tanner Stage 2 or 2) has undergone a hysterectomy or bilateral oophorectomy.

Female Child of Childbearing Potential and/or Parent/Guardian:

1. I have verified and counseled the subject and/or parent/guardian regarding the following:
 - Potential risk of fetal exposure to lenalidomide: A teratogenic potential of lenalidomide in humans cannot be ruled out. If lenalidomide is taken during pregnancy, it may cause birth defects or death to any unborn baby. Females are advised to avoid pregnancy while taking lenalidomide. Female children of childbearing potential must agree not to become pregnant while taking lenalidomide.
 - That the required pregnancy tests performed are negative.
 - The subject confirmed that she is using TWO reliable methods of birth control at the same time, or complete abstinence (True abstinence is acceptable when this is in line with the preferred and usual lifestyle of the subject. Periodic abstinence [eg calendar, ovulation, symptothermal or post-ovulation methods] and withdrawal are not acceptable methods of contraception.) from heterosexual contact (at least 28 days prior to receiving lenalidomide, while receiving lenalidomide, during dose interruptions and for at least 28 days after the last dose of lenalidomide).

One highly effective method and one additional method of birth control must be used AT THE SAME TIME. The following are examples of highly effective and additional effective methods of contraception:

Examples of highly effective methods:

- Intrauterine device (IUD)
- Hormonal (birth control pills, injections, implants, levonorgestrel-releasing intrauterine system [IUS], medroxyprogesterone acetate depot injections, ovulation inhibitory progesterone-only pills [e.g. desogestrel])
- Tubal ligation
- Partner's vasectomy

Examples of additional effective methods:

- Male condom
- Diaphragm
- Cervical Cap

- The subject confirmed that even if she has amenorrhea she must comply with advice on contraception.
- Pregnancy tests before, during administration of lenalidomide and at the last dose of lenalidomide, even if the subject agrees not to have reproductive heterosexual contact.
- Frequency of pregnancy tests to be done:

Two pregnancy tests will be performed prior to receiving lenalidomide, one within 10 to 14 days, and a second within 24 hours of the start of lenalidomide.

Every week during the first 28 days of this study and a pregnancy test every 28 days while the subject is taking lenalidomide if menstrual cycles are regular.

Every week during the first 28 days of this study and a pregnancy test every 14 days while the subject is taking lenalidomide if menstrual cycles are irregular.

If the subject missed a period or has unusual menstrual bleeding.

When the subject is discontinued from the study and at Day 28 after the last dose of lenalidomide if menstrual cycles are regular. If menstrual cycles are irregular, pregnancy tests will be done at discontinuation from the study and at Days 14 and 28 after the last dose of lenalidomide.

- The subject confirmed that she will stop taking lenalidomide immediately in the event of becoming pregnant and to call her study doctor as soon as possible.

- The subject confirmed that she has not and will not breastfeed a baby while taking lenalidomide and for at least 28 days after the last dose of lenalidomide.
- The subject has not and will never share lenalidomide with anyone else.
- The subject has not and will not donate blood while taking lenalidomide, during dose interruptions and for at least 28 days after the last dose of lenalidomide.
- The subject has not and will not break, chew, or open lenalidomide capsules at any point.
- The subject confirmed that she will return unused lenalidomide capsules to the study doctor.

2. I have provided the Lenalidomide Information Sheet to the subject.

Female Child Not of Childbearing Potential:

- 1. I have verified and counseled the female child NOT of childbearing potential and/or her parent/guardian regarding the following:
 - The need to be aware of signs of menarche and inform site staff as soon as possible regarding onset, if it occurs.
 - Potential risk of fetal exposure to lenalidomide: A teratogenic potential of lenalidomide in humans cannot be ruled out. If lenalidomide is taken during pregnancy, it may cause birth defects or death to any unborn baby.
 - The subject has not and will never share lenalidomide with anyone else.
 - The subject has not and will not donate blood while taking lenalidomide, during dose interruptions and for at least 28 days after the last dose of lenalidomide.
 - The subject has not and will not break, chew, or open lenalidomide capsules at any point.
 - The subject confirmed that she will return unused lenalidomide capsules to the study doctor.

2. I have provided the Lenalidomide Information Sheet to the subject.

Do Not Dispense Lenalidomide if:

- The subject is pregnant.
- No pregnancy tests were conducted for a FCCBP.
- The subject states she did not use TWO reliable methods of birth control (unless practicing complete abstinence from heterosexual contact) at least 28 days prior to receiving lenalidomide, while receiving lenalidomide and during dose interruptions.

- The subject stated that she has or does not want to adhere to pregnancy precautions outlined within this PPP.

Counselor Name (Print): _____

Counselor Signature: _____ Date: ____ / ____ / ____

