Following completion of training, the designated counselors will be responsible for counseling subjects prior to any treatment or the dispensing of lenalidomide to ensure that the subject has complied with all requirements including use of birth control and pregnancy testing and that the subject understands the risks associated with lenalidomide. Information pertinent to the risks of lenalidomide that should be used as part of training can be found in the document entitled "Lenalidomide Risks of Fetal Exposure, Pregnancy Testing Guidelines and Acceptable Birth Control Methods" ([Appendix II](#)). All investigators should be familiar with this document and the risks associated with lenalidomide. Counseling must be documented by the completion of a Lenalidomide Education and Counseling Guidance Document ([Appendix III](#)). No drug will be dispensed until counseling and completion of this document occurs. A copy of this document must be maintained in the patient's medical record. Counseling includes verification with the patient that required pregnancy testing was performed and results were negative. Pregnancy test results should be documented on the Lenalidomide Patient Card for Pediatric Patients ([Appendix IV](#)). A Lenalidomide Information Sheet ([Appendix V](#)) will be supplied with each medication dispense.

Please Note: The counseling requirements for investigational use of lenalidomide are separate from the RevAssist program requirements in the United States and the RevAidSM program in Canada. Participation in these two programs is not required, nor sufficient for use of the investigational lenalidomide product.

All clinical and laboratory studies to determine eligibility must be performed within 7 days prior to enrollment unless otherwise indicated in the eligibility section below.

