VASCULAR DISORDERS - Hot flashes; Phlebitis; Vascular disorders - Other (hemorrhage NOS)

Note: Lenalidomide (CC-5013) in combination with other agents could cause an exacerbation of any adverse event currently known to be caused by the other agent, or the combination may result in events never previously associated with either agent.

Effect in Pregnancy and Lactation:

Lenalidomide is **Pregnancy category X**. It can cause fetal harm when administered to a pregnant woman and is contraindicated in women who are or may become pregnant. There are no adequate and well-controlled studies in pregnant women. However, in an embryofetal developmental toxicity study in monkeys, teratogenicity, including thalidomide-like limb defects occurred in offspring when pregnant monkeys received oral lenalidomide during organogenesis at doses approximately 0.17 times the adult maximum recommended human dose (MRHD) of 25 mg, based on BSA. Similar studies in pregnant rabbits and rats at 20 times and 200 times the MRHD respectively, produced embryoletality in rabbits and no adverse reproductive effects in rats. In another study, pregnant rats received lenalidomide from organogenesis through lactation; some delay in sexual maturation occurred in male offspring. As with thalidomide, the rat model may not adequately address the full spectrum of potential human embryofetal developmental effects for lenalidomide.

The requirements of this study and the requirements to receive the commercially available supply are slightly different. For the purpose of this study, female of childbearing potential (FCBP) is a sexually mature (at least Tanner 2) female who: 1) has achieved menarche or breast development in Tanner Stage 2 or greater, and 2) has not undergone a hysterectomy or bilateral oophorectomy and must use effective means of contraception for 28 days before therapy, during lenalidomide therapy and dose interruptions, and for 28 days following discontinuation of lenalidomide therapy or continually abstain from reproductive heterosexual intercourse. Venous thromboembolism (VTE) has been seen in patients with multiple myeloma receiving lenalidomide plus dexamethasone and patients with myelodysplastic syndrome receiving lenalidomide monotherapy (to a lesser extent). Because oral contraceptives may also place the patient at risk of VTE, physicians should discuss this increased risk and the risk/benefit of contraceptive methods with patients receiving lenalidomide.

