If no, please list all the protocols #(s), corresponding CTEPsiteID(s) and institution names(s) that you *plan to provide* counseling for:

If yes, please list the protocols #(s), corresponding CTEPsiteID(s) and institution names(s) *for protocols Celgene has already associated you with*:

Protocol#:	CTEPsiteID	Institution

APPENDIX II: LENALIDOMIDE RISKS OF FETAL EXPOSURE, PREGNANCY TESTING GUIDELINES AND ACCEPTABLE BIRTH CONTROL METHODS

Risks Associated with Pregnancy

Lenalidomide was teratogenic in both rats and rabbits when administered during the period of organogenesis. Thalidomide is a known human teratogen that causes severe life-threatening human birth defects. If Lenalidomide is taken during pregnancy, it may cause birth defects or death to an unborn baby.

Definition of female children of childbearing potential (FCCBP)

A FCCBP is a female child who:

- Has achieved menarche and/or breast development in Tanner stage 2 or greater
 - Onset of fertility typically occurs within 3-12 months after menarche. Menarche varies considerably from person to person, and thus no age cut off can be attributed. One of the primary tools used to follow a girl's progress through puberty is the Tanner staging system which describes the pattern of development of the secondary sex characteristics. Tanner stage 2 corresponds to the beginning of breast development, which is the first visible sign of puberty in girls. Breast development is estrogen stimulated, and since ovulation cannot occur without estrogen, Tanner stage 2 will be a reliable marker for the definition of fertility.
- Has not undergone a hysterectomy or bilateral oophorectomy.

Note: Amenorrhea following cancer therapy does not rule out childbearing potential

Definition of Female Children NOT of Childbearing Potential (FCNCBP)

A FCNCBP is a female child who:

- has **not** yet experienced menarche or breast development has not reached Tanner stage 2 or
- has undergone a hysterectomy or bilateral oophorectomy.

Counseling

Female Children of Childbearing Potential (FCCBP)

For a, FCCBP lenalidomide is contraindicated unless all of the following are met (i.e., all female children of childbearing potential must be counseled concerning the following risks and requirements prior to the start of lenalidomide):

- She understands the potential teratogenic risk to the unborn child

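### Appendices II and III A join the two non-childbearing conditions with *or* where *and* is needed, so a premenarchal girl at Tanner stage 2 or above falls in both classes

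*Combined protocol and SAP*

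**What the plan says.** **Childbearing class (FCCBP).** Appendix II's criterion is "Has achieved menarche and/or breast development in Tanner stage 2 or greater", in a girl who has had neither hysterectomy nor bilateral oophorectomy. Appendix III A prints *or* in place of *and/or*, which is logically the same.

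**Non-childbearing class (FCNCBP).** Appendix II describes a girl who has not "yet experienced menarche or breast development has not reached Tanner stage 2", or who has had one of those operations. Appendix III A repeats this: a girl who "has not experienced menarche or breast development has not reached Tanner Stage 2", or who has had surgery.

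**Stated intent.** Appendix II justifies the Tanner criterion by saying that "Tanner stage 2 will be a reliable marker for the definition of fertility". Section 6.1, in the definition it sets for this study, says that a female of childbearing potential "is a sexually mature (at least Tanner 2) female who" meets the menarche or breast-development criterion and has not had surgery.

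**Use of the classes.**
- The Appendix III A form is completed before each dispensing. The counselor ticks one risk category, and no tie-break is given.
- Section 3.1.5.1 makes the completed form auditable, forbids dispensing without it, and says: "Counseling includes verification with the patient that required pregnancy testing was performed and results were negative".
- On the form, the line "That the required pregnancy tests performed are negative" is printed on the FCCBP track only.
- Both tracks share one list of reasons not to dispense, which includes "No pregnancy tests were conducted for a FCCBP".
- The Appendix IV patient card is completed by the investigator, who under Section 3.1.5.1 may not be the counselor. For the FCNCBP class it says that pregnancy tests need not be monitored.

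**The concern.** The FCNCBP class should be the negation of the FCCBP class. To negate *menarche or Tanner 2*, both markers must be absent. Both appendices instead let the absence of either one suffice. The girl caught by this is the one the Tanner criterion exists to protect: before menarche, only her Tanner stage can place her in the childbearing class.

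What is at stake is a safeguard for a teratogenic drug, not an estimate or a test. A counselor who ticks FCNCBP for such a girl can point to the printed wording, and her track then has no prompt to verify a negative test. The investigator's card is a separate decision. However, Section 3.1.5.1 tells investigators to be familiar with Appendix II, which carries the same wording, so both people can meet the same error. Treatment may last 26 cycles of 28 days (26 × 28 = 728 days, about two years) in patients under 22, so a girl could pass Tanner 2 before menarche while on therapy.

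**Working it through.** The plan gives no figure to reproduce; this is a logic check. Let M = menarche reached, T = breast development at Tanner 2 or above, S = hysterectomy or bilateral oophorectomy. From Appendices II and III A:

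- FCCBP = (M or T) and not S
- FCNCBP as printed = (not M or not T) or S
- FCNCBP with *and* = (not M and not T) or S

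| M | T | S | FCCBP | FCNCBP as printed | FCNCBP with *and* |
|---|---|---|---|---|---|
| no | no | no | no | yes | yes |
| no | no | yes | no | yes | yes |
| no | yes | no | **yes** | **yes** | no |
| no | yes | yes | no | yes | yes |
| yes | no | no | **yes** | **yes** | no |
| yes | no | yes | no | yes | yes |
| yes | yes | no | yes | no | no |
| yes | yes | yes | no | yes | yes |

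As printed: 3 rows are FCCBP, 7 are FCNCBP and 2 are both (3 + 7 − 2 = 8). With *and*: 3 + 5 = 8, so no row is in both classes and none is in neither. The first overlapping row (premenarchal, Tanner 2 or above, no surgery) is the realistic one. The second (menarche reached, below Tanner 2) would be rare.

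Next, what the form does after an FCNCBP tick. Its FCNCBP track has 6 counseling items: awareness of menarche, fetal risk, not sharing, not donating blood, not opening capsules, and returning unused capsules. None concerns pregnancy tests. The common list has 4 reasons not to dispense: pregnancy, no tests done in an FCCBP, two contraceptive methods not used (unless abstinent), and unwillingness to follow the precautions. One of the 4 is tied to FCCBP status, but to the status itself and not to the box ticked.

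Finally, what the rest of the protocol still requires of the girl in the first overlapping row:

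| Provision | Depends on childbearing potential? | Covers her on its text? |
|---|---|---|
| Testing duties (3.1.5, 4.1, 7.1, Appendix II) | Yes | Yes, she meets FCCBP |
| Cycle 1 start test (4.3) | Yes | Yes, she meets FCCBP |
| Later cycle-start test (4.3) | No limit printed there | Yes |
| Two-method rule for sexually active females (3.2.9.3) | No | Yes, if sexually active |
| Missing-test dispensing stop (Appendix III A) | Yes | Yes, she meets FCCBP |
| Negative-test counseling line (Appendix III A) | Printed on the FCCBP track | Not on her track if FCNCBP is ticked |
| Test monitoring on the patient card (Appendix IV) | Separate investigator entry | Not required if entered as FCNCBP |

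**The case against.** The strongest reply is that the overlap cancels nothing. Testing duties attach to females of childbearing potential, this girl meets that definition wherever it is printed, and also meeting the other one does not release her. The FCNCBP wording appears only in the appendices. The sentence is loosely built and can be taken to mean *neither*. It stands next to an FCCBP definition that names her Tanner stage, and the form reprints that definition each time. Counselors must complete pediatric training, though its content is not shown. For monitoring on the card to be dropped, the investigator must also misclassify her.

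Most of this stands. It rules out two stronger inferences that a reader might draw. One is that an FCNCBP tick in itself waives pregnancy testing or contraception; no section says so. The other is that the missing-test stop lapses with the tick. That stop is in the common list and, on its text, covers any girl who is in fact FCCBP. Only the negative-test counseling line is truly specific to the track.

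The reply does not remove the defect. The second clause has its own verb and its own negation, so the literal sense is *or*. Section 3.1.5 sends readers to Appendix II for the meaning of childbearing potential, where the faulty counterpart is also printed. Duties that depend on a class protect a girl only if she is put in that class.

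**Conclusion.** The wording is wrong in both appendices and contrary to the stated intent. For the premenarchal girl at Tanner 2 or above, that intent is explicit in Section 6.1 and Appendix II. For the rare postmenarchal girl below Tanner 2, it follows from the appendices' own FCCBP criterion.

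The size is 2 of 8 logical combinations in both classes, against 0 when corrected. These are combinations, not patients. The documents do not give the number of girls affected. The 39 females expected among 80 patients (Section 9.12) are only a ceiling, and that count includes girls whom the wording classifies without ambiguity. No estimate of harm is possible.

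The practical risk is limited. It rests on a counselor, an investigator or both following the literal FCNCBP text, and on duties tied to childbearing potential then not being applied to that girl. It should still be corrected, because it is an operative rule on a form completed before every dispensing of a teratogen. It has no bearing on endpoints, sample size or analysis.

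**What to change.** In Appendices II and III A, change the *or* between the menarche condition and the breast-development condition to *and*. Keep the later *or* before the surgical clause, which is correct. The class then reads, in substance: no menarche **and** breast development below Tanner stage 2; **or** previous hysterectomy or bilateral oophorectomy. The two classes become exact complements.

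The edit is one word in each appendix. Because the form is auditable and in use at sites, the real cost is a minor amendment and a replacement form.

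A separate, optional edit, not part of this defect, would extend the FCNCBP prompts in both appendices, which ask only about menarche, to cover onset of breast development as well.

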**Maintain a copy of the Education and Counseling Guidance Document in the patient records. **

APPENDIX III B: LENALIDOMIDE EDUCATION AND COUNSELING GUIDANCE DOCUMENT FOR MALE SUBJECTS

To be completed prior to each dispensing of lenalidomide.

Protocol Number: ACNS1022

COG Patient ID#: _____ DOB: ____ / ____ / ____ (mm/dd/yyyy) \

1. I have verified and counseled the male subject and/or his parent/guardian regarding the following:

- Potential risks of fetal exposure to lenalidomide: A teratogenic potential of lenalidomide in humans cannot be ruled out. If lenalidomide is taken during pregnancy, it may cause birth defects or death to any unborn baby.
- The subject confirmed that he has practiced complete abstinence (True abstinence is acceptable when this is in line with the preferred and usual lifestyle of the subject. Periodic abstinence [eg calendar, ovulation, symptothermal or post-ovulation methods] and withdrawal are not acceptable methods of contraception.) or used a condom when engaging in sexual contact (including those who have had a vasectomy) with a pregnant female or a female of childbearing potential, while taking lenalidomide, during dose interruptions and for at least 28 days after the last dose of lenalidomide.
- The subject confirmed that he has not impregnated his female partner while in the study.
- The subject confirmed that he will notify his study doctor if his female partner becomes pregnant and the female partner of a male subject taking lenalidomide confirmed that she will call her healthcare provider immediately if she becomes pregnant.
- The subject has not and will never share lenalidomide with anyone else.
- The subject confirmed that he has not donated and will not donate semen or sperm while taking lenalidomide or during dose interruptions and that he will not donate semen or sperm for at least 28 days after the last dose of lenalidomide.
- The subject has not and will not donate blood while taking lenalidomide, during dose interruptions and for at least 28 days after the last dose of lenalidomide.
- The subject has not and will not break, chew, or open lenalidomide capsules at any point.
- The subject confirmed that he will return unused lenalidomide capsules to the study doctor.

2. I have provided the Lenalidomide Information Sheet to the subject.

Do Not Dispense Lenalidomide if:

- **The subject stated that he has or does not want to adhere to pregnancy precautions outlined within this PPP.**

